6.1 Investigational Product/Placebo Supply

SHR0302 and matching placebo tablets will be provided by the sponsor and dispensed for oral administration. Subjects will be randomized to receive 4mg QD, 4mg BD, 8mg QD or Placebo in a ratio of 1:1:1:1 respectively for the first 8 week of treatment phase. Subjects randomized into placebo in treatment phase will also have a pre-assigned randomized treatment sequence for extension phase, which are 3 active groups (placebo -> 4mg QD, placebo -> 4mg BD, and placebo -> 8mg QD) in a 1:1:1 ratio. Subjects randomized to the active arms for treatment phase will remain in the same dose group in the extension phase.

SHR0302 will be provided as combination of 4mg tablets, including the matching placebo by the Sponsor. At study visits on Day 0, and Week 4, sufficient trial medication will be dispensed to complete dosing for four weeks.

For subjects enrolled into the blinded active arm extension phase, trial medications will be dispensed at week 8 and week 12, where trial medications will be dispensed sufficient for 4 weeks. At visits Week 4, Week 8, Week 12, and Week 16 (end of extension phase), or at follow-up visit/contact if the subject is withdrawn, the subject must return all trial medication and the amount returned will be recorded.

Note that only those patients enrolled into the extension phase will be dispensed with trial medications at week 8 and week 12.

6.1.1 Study Drug Dispensing

Investigational product will be assigned to subjects at the baseline visit once successfully randomized through the tele-randomization system. The investigator or appropriate delegate at the site will access the tele-randomization system (IVRS) at baseline visit to receive correct container numbers to be dispensed to the subject. All medication dispensed or returned will be documented in the eCRF.

After the completion of first 8-week treatment phase, all completers may be enrolled into the extension phase according to the group they were randomized to for the extension phase.

6.1.2 Study Drug Administration

Study medication will be self-administered by the subject twice daily, one (2 tablets) in the morning, another (2 tablets) in the afternoon. Approximately 8 - 12 hours between the morning and afternoon doses.

However, at baseline (Day 0) the first dose will be taken in the clinic. At Week 4 and at the end of treatment (Week 8) subjects should take their morning oral dose at the clinic. Study medication may be taken with or without food.

6.2 Treatment Assignment

Subjects will be randomized into the trial in a 1:1:1:1 allocation ratio to SHR0302 8mg QD, placebo, SHR0302 4mg QD or SHR0302 4mg BD for the treatment phase provided they have satisfied all inclusion/exclusion criteria. Subjects will be stratified according to whether or not they have had previous exposure to anti-TNF α /biological treatment and randomized at baseline according to a computer generated pseudo random code using the method of permuted blocks balanced within each randomization strata. Subjects randomized into placebo in treatment phase will also have a pre-assigned randomized treatment sequence for extension phase, which are 3 active groups (placebo -> 4mg QD, placebo -> 4mg BD, and placebo -> 8mg QD) in a 1:1:1 ratio. Subjects randomized to the active arms for treatment phase will remain in the same dose group in the extension phase.

After the completion of treatment phase, subject may choose to enroll into the extension phase according to the group they were randomized to for the extension phase. All the subjects that have completed the first treatment phase have the option not entering into the extension phase after first 8 weeks of treatment. Early withdrawn subjects during the first treatment phase cannot enter the extension phase.

6.3 Blinding

Investigational product taken during the 8-week treatment period will be double-blind. Neither the subject nor the study physician will know which study medication the subject is receiving. In the subsequent 8-week extension phase, although subjects are given active treatments, both the subjects and investigators are blinded to which dose of SHR0302 they are randomized to.

In order to preserve blinding and ensure patients compliance throughout the study, the study drug packaging has been designed with detailed consideration. All the arms are administered under twice daily (BD) dosing regime and placebo is used according to the schedule in the table below. ([Table 2](#))

Table 2. Study drug packaging design for treatment arms

Study Arms-all BID	Dose 1 (am)	Dose 2 (pm)
4mg qd	4mg+ placebo	Placebo + placebo
8mg qd	4mg+ 4mg	Placebo + placebo
4mg bd	4mg +placebo	4mg +placebo
placebo	Placebo + placebo	Placebo + placebo

At each dosing time (morning, am or afternoon, pm), subject will be taking two tablets. In one day, a subject will take a total of four tablets, two tablets in the morning and two tablets in the afternoon.

The investigator or treating physician may unblind a subject's treatment assignment **only in the case of an emergency**, when knowledge of the study treatment is essential for the appropriate clinical management or welfare of the subject. Whenever possible, the investigator must first discuss options with the Reistone Biopharma/designated CRO Medical Monitor or appropriate Reistone Biopharma/designated CRO study personnel **before** unblinding the subject's treatment assignment. If this is impractical, the investigator must notify Reistone Biopharma/designated CRO as soon as possible, but without revealing the treatment assignment of the unblinded subject, unless that information is important for the safety of subjects currently in the study. The date and reason for the unblinding must be recorded in the appropriate data eCRF.

Reistone Biopharma/designated CRO staff may unblind the treatment assignment for any subject with an SAE. If the SAE requires that an expedited regulatory report be sent to one or more regulatory agencies, a copy of the report, identifying the subject's treatment assignment, may be sent to clinical investigators in accordance with local regulations. Subjects will be withdrawn if the treatment code becomes unblinded. The primary reason for discontinuation (the event or condition which led to the unblinding) will be recorded in the eCRF.

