5.6 Withdrawal Criteria

A subject may withdraw from the study at any time at their own request, or they may be withdrawn at any time at the discretion of the investigator or Reistone Biopharma for behavioral or administrative reasons.

If a subject develops a serious infection during the study, defined as any infection (viral, bacterial, and fungal) requiring hospitalization or parenteral antimicrobials, he/she must be discontinued from the study.

All abnormal laboratory events of clinical significance should be followed until the laboratory values have returned to normal or baseline levels. In addition, any subject with a confirmed increase in serum creatinine at the end of study or at discontinuation of at least 0.2 mg/dL and at least 10% above the average of screening and baseline value will be followed up with retesting every one to two weeks until the creatinine elevation has fully reversed to within 10% of the subject's baseline value or has stabilized.

If a subject has any clinically significant, study-related abnormalities at the conclusion of the study, the medical monitor (or designated representative) should be notified and every effort should be made to arrange follow-up evaluations at appropriate intervals to document the course of the abnormalities.

The reason for a subject discontinuing from the study will be recorded in the eCRF. A discontinuation occurs when a randomized subject ceases participation in the study, regardless of the circumstances, prior to completion of the protocol. The investigator must determine the primary reason for discontinuation. Withdrawal due to adverse events should be distinguished from withdrawal due to insufficient response according to the definition of adverse event noted in [Section 7.3.11](#). The final evaluation required by the protocol will be performed at the time of the study discontinuation. The investigator will record the reason for study discontinuation, provide or arrange for appropriate follow-up if required.

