5.8 Early Withdrawal

The definition of an early subject withdrawal from the study will be any subject who is randomized to double-blind medication and, for any reason, is withdrawn prior to completion of the Visit 5 procedures.

A subject may voluntarily discontinue participation in the study at any time. The investigator may also, at his/her discretion; discontinue the subject from participating in the study at any time. In addition, the investigator must make every effort to have the subject return to the clinic as soon as possible after discontinuation of study drug for an Early Withdrawal Visit. An Early Withdrawal Visit may occur at a regular scheduled clinic visit or between clinic visits. The following evaluations and procedures should be completed and recorded in the eCRF.

- Concomitant medication assessment
- AE/SAE assessment

- Physical examination (recorded in source documents only)
- Vital signs
- Collect and review electronic diary
- Collect used study medication (blinded study medication)
- Assess compliance with investigational drug
- 12-Lead ECG
- Laboratory assessments (including chemistry, haematology, and pregnancy test for females of childbearing potential and routine urinalysis)
- Call IVRS to report subject's early withdrawal from the study
- Endoscopy, Mayo score, 9-point modified Mayo score, and partial Mayo score, if feasible.

A subject that is withdrawn from the study after being randomised to treatment cannot be re-screened and subjects who are withdrawn from the study will not be replaced. If the subject withdraws from the study, and also withdraws consent for disclosure of future information, no further evaluations should be performed, and no additional data should be collected. The sponsor may retain and continue to use any data collected before.

Thyroid specific criteria:

Subjects with deranged TSH level (outside of normal range) only, but normal free T4 or free T3. Investigator can follow-up the subject with thyroid function test and assess clinically in 4 weeks.

Deranged TSH level, with associated deranged free T4 and/or free T3(outside of normal range), the investigator should assess subject's clinical condition and decide if the subject should be withdrawn.

Subject with signs and/or symptoms suggestive of hypothyroidism or hyperthyroidism should have laboratory thyroid function performed. If any of the thyroid parameters (TSH, free T4, or free T3) were outside of normal range, the subject is to be withdrawn.

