5.9 Stopping Criteria

The stopping safety criteria are as below: Subject who fulfil the following criteria should discontinue the study.

- Liver chemistry threshold stopping criteria have been designed to assure subject safety and to evaluate liver event etiology (in alignment with the FDA premarketing clinical liver safety guidance) Study treatment will be stopped if the liver chemistry stopping criteria is met. Refer to [Section 7.3.9 Liver Chemistry Stopping and Follow-up Criteria](#).
- A subject that meets the QTc criteria below will be withdrawn from the study. The QT correction formula used to determine discontinuation should be the same one used throughout the study.

-QTc, QTcB/QTcF > 500 ms

-Change from baseline: QTc >60 ms

Use the averaged QTc values of the 3 ECGs to determine whether the subject should be discontinued from the study.

- Abnormal laboratory values of interests. (modified from CTCAE 5.1 criteria)
 - Hemoglobin (Hgb) <7.0 g/dL; or when blood transfusion is indicated.
 - Neutrophil count < 500/mm³
 - Platelet count < 25,000/mm³
 - Lymphocyte count < 200/mm³
 - Leukocyte count < 2000/mm³
- Subject who develops Venous Thrombosis (eg Deep Vein Thrombosis).
- Subject who develops Pulmonary Embolism.
- Subject who develops Cerebrovascular Events (eg Thromboembolic Stroke, Transient Ischemic Attack (TIA), Myocardial Infarction)
- An unacceptable adverse event, as determined by the Investigator and the medical monitor.
- Any unacceptable adverse event that is thought to be related to the investigational product may result in the study being terminated.
- Significant protocol deviation. The discovery that post-randomization the subject failed to meet protocol entry criteria or did not adhere to protocol requirements, and continued participation poses an unacceptable risk to the subject's health.
- If the subject is found to be pregnant, the subject must be withdrawn immediately. The procedure is described in [Section 7.3.10](#).

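### Protocol 6.3 withdraws a subject whenever the treatment code is broken and makes no exception for a sponsor-only code break after an SAE, so a subject who is still blinded can be lost before Week 8

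*Protocol*

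**What the plan says.** Protocol 6.3 describes the blind as that of the subject and the physician: "Neither the subject nor the study physician will know which study medication the subject is receiving". It gives two routes to breaking the code. The investigator or treating physician may do so in an emergency. Separately, "Reistone Biopharma/designated CRO staff may unblind the treatment assignment for any subject with an SAE"; this route is not limited to emergencies or to events needing expedited reporting. If an expedited report is required, a copy showing the assignment may go to investigators, so disclosure to the site is optional.

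The same paragraph continues: "Subjects will be withdrawn if the treatment code becomes unblinded". The event that led to the unblinding is then recorded in the eCRF as the main reason for discontinuation.

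The consequences are set out elsewhere:

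- Protocol 5.8 counts as an early withdrawal any randomized subject who, for any reason, "is withdrawn prior to completion of the Visit 5 procedures". Withdrawn subjects are not replaced.
- Protocol 6.2: "Early withdrawn subjects during the first treatment phase cannot enter the extension phase".
- SAP 15.1.1 treats a patient who lacks any Mayo subscore at the assessed visit as a failure.
- SAP 6.5 applies no visit windowing.

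**The concern.** Withdrawal after a code break makes sense when the person treating or reporting on the subject learns the assignment. A confidential look by sponsor or CRO staff does not have that effect: the two parties whose blind 6.3 describes are still blinded. Withdrawing the subject then protects nothing. It stops treatment, closes the extension, and normally turns a possible Week 8 responder into an NCF failure because of an administrative act by the sponsor. What is at stake is valid Week 8 data from a subject who could have continued.

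**Working it through.** **1. Is there an exception?** None was found in Protocol 5.6, 5.8, 5.9, 6.3, 7.3.10 or 7.3.14, or in the SAP. Since passing the assignment to investigators is optional and mentioned only for expedited reports, 6.3 itself allows a break known only to the sponsor or CRO, and the withdrawal sentence does not set that case apart.

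**2. Which subjects does it affect?** Only those with an SAE before Week 8 that would not have ended participation anyway. For a serious infection, Protocol 5.6 already says "he/she must be discontinued from the study". Protocol 5.9 lists liver criteria, low blood counts, thrombosis, pulmonary embolism and cerebrovascular events, and also: "An unacceptable adverse event, as determined by the Investigator and the medical monitor". Other SAEs can be compatible with continuing.

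**3. What happens in the analysis?** The subject stays in the full analysis set. Endoscopy and Mayo scores are collected at the early-withdrawal visit if feasible, and "An Early Withdrawal Visit may occur at a regular scheduled clinic visit or between clinic visits". A visit between scheduled visits is not mapped to Week 8, so the Week 8 subscores are normally missing and the subject counts as a failure.

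**4. How many?** The documents give no SAE or unblinding rate, so the following are assumptions: 3% to 5% of subjects have an SAE, spread evenly over 18 weeks, and half of the early cases drop out of the count because the event stops participation or nobody unblinds.

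- Subjects with an SAE before Week 8: 152 × 0.03 × 8/18 = 2.0; 152 × 0.05 × 8/18 = 3.4.
- Mean planned response (Protocol 9.2.1): (57 + 57 + 50 + 30)/4 = 48.5%.
- Would-be responders among them: 2.0 × 0.485 = 1.0; 3.4 × 0.485 = 1.6.
- After halving: 0.5 to 0.8, so about one or fewer.

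**5. Against the dropout allowance.** Protocol 9.2.1 allows 8%: 0.08 × 152 = 12.2, in line with 152 randomized for 140 evaluable. Even the unhalved 2.0 to 3.4 subjects fit within it.

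**6. Power.** The plan states 80% global power with 35 evaluable per arm. Three pairwise Mantel-Haenszel chi-square tests against a shared placebo arm, unstratified, at the planned rates with Hochberg cut-offs 0.1, 0.05 and 0.0333, give 80.1%, so the figure reproduces. With all 152/4 = 38 per arm analysed, power is 79.0%. If one subject in 152 becomes a failure (all rates multiplied by 1 − 1/152), it is 78.6%. That 0.4-point change cannot be told apart from the discreteness of the test: the same calculation gives 76.2% at 36 per arm, 77.6% at 37 and 80.9% at 39.

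**The case against.** The strongest reply is that 6.3, read as a whole, is about losing the site's blind. The withdrawal sentence follows directly on the one about sending investigators a report that shows the assignment. The reason for discontinuation goes into the eCRF, and Protocol 5.6 makes determining it the investigator's task. A confidential look gives the site nothing to act on. SAP 4.2 points the same way: an unblinded sponsor team receives results once all patients have had the opportunity to complete Week 8, when some may still be in the extension, and nobody is withdrawn for that. This stands as the probable intent, but the sentence does not say it, and sites and CRO staff have to follow the text.

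It is also fair that sponsor unblinding is permitted rather than required, that many SAEs end participation anyway, and that the number affected could be zero. The dropout allowance covers the count. The per-protocol set (SAP 5.4) excludes patients without Week 8 efficacy data, and the sensitivity analysis in SAP 15.1.2 (LOCF, with baseline carried forward for endoscopy) does not impose automatic failure. All of this limits the size of the problem; none of it removes the missing exception.

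A reader might go further and infer that every SAE leads to withdrawal, or that the rule materially weakens the primary comparison. The documents support neither. The unblinding sentence is permissive, no rate is given, and the loss worked out above is too small to resolve. A reader might also infer that sponsor code breaks must be restricted to expedited reports and handled outside the study team. That is a separate governance choice, which this defect does not require.

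**Conclusion.** The point holds as a minor one. A stated rule in 6.3, applied as written, can withdraw a subject whose own blind and whose investigator's blind are intact. Before Week 8 this normally produces an NCF failure and bars the extension. The expected cost is about one would-be responder or fewer, resting on an assumed 3% to 5% SAE rate, an even spread over 18 weeks and an assumed halving. If it did happen, one subject is at most 1/38 = 2.6 percentage points of an arm's response rate. The validity of the trial is not in question.

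**What to change.** Reword the withdrawal sentence in Protocol 6.3 to say: subjects will be withdrawn if their assignment becomes known to the investigator, treating physician, other site staff or the subject; a confidential sponsor or CRO code break for safety reporting does not require withdrawal, and treatment and Week 8 assessments continue.

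Withdrawal after a break that reaches the site or the subject stays as it is. The cost is one sentence in the protocol. Sample size, alpha, planned power and the SAP analyses need no change.

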6.4 Drug Storage and Accountability

SHR0302 must be stored according to the labeled storage conditions in a locked area with restricted access. The investigator or appropriate delegate at the site (eg pharmacist), will ensure that all study drug is stored in a secured area, under recommended storage condition, and in accordance with regulatory requirements.

The investigator must maintain adequate records documenting the receipt, use, loss, or other disposition of the investigational product(s). To ensure adequate records, all drug supplies will be accounted for in the drug accountability inventory forms as instructed by Reistone Biopharma/designated CRO and will be monitored by counting of unused medications returned by the subject at Week 4, 8, 12 and 16 or at follow-up visit/contact if the subject is withdrawn.

At the end of trial, Reistone Biopharma/designated CRO will provide instructions as to the disposition of any unused investigational product. If Reistone/designated CRO authorizes destruction at the trial site, the investigator must ensure that the materials are destroyed in compliance with applicable environmental regulations, institutional policy, and any special instructions provided by Reistone Biopharma/designated CRO. Destruction must be adequately documented. SHR0302 will not be made available to subjects at the end of study.

6.5 Treatment Compliance

Investigational product compliance will be assessed by the site at each clinic visit following

baseline (Day 0) up to the end of treatment. Non-compliance is defined as taking less than 80% of study drug products as directed by the dosing instructions. The investigator has the discretion to withdraw any subject from the study for reasons of non-compliance with the dosing regimen. Investigators should indicate on the appropriate eCRF page noncompliance with study treatment and provide an explanation.

Inventory control of all study medications must be rigorously maintained throughout the duration of the study until all medication has been accounted for and returned to the sponsor. Any discrepancies noted between drug dispensing records and the drug inventory must be reported to Reistone Biopharma/designated CRO.

6.6 Concomitant Medications

6.6.1 Permitted Concomitant Medications

All concomitant medication(s) taken during the trial must be recorded with indication, daily dose, and start and stop dates of administration. All subjects will be questioned about concomitant medication at each clinic visit. Following therapy for ulcerative colitis are allowed providing they are stable for the specified period of time:

- Oral 5-ASA or sulfasalazine are allowed providing that the dose is stable for at least 2 weeks prior to baseline and during the study treatment period.
- Oral steroids are allowed during the study up to the dose of 30 mg/day of prednisolone or equivalent, providing that the dose has not been commenced or changed within 2 weeks of baseline and until to the end of treatment phase (Week 8). During the treatment phase, if the subject cannot tolerate the oral steroids dose or there is a significant safety risk associated with continued use of the steroids, the dose may be reduced at the discretion of the investigator and the reasons for dose reduction need to be documented in the medical records. During the extension phase, tapering of the oral steroid dose can be commenced for subjects at investigator's discretion. Tapering scheduled treatment is provided as below:
 - Subjects receiving > 10 mg/day prednisolone or equivalent: taper dose by 5 mg/week until a 10 mg/day dose (or equivalent) is reached, then continue tapering at 2.5 mg/week until 0 mg/day.
 - Subjects receiving ≤ 10 mg/day prednisolone or equivalent: taper dose by 2.5 mg/week until 0 mg/day.

If subject experiences worsening of signs or symptoms during the tapering schedule, in the opinion of the investigator, due to reduction in oral steroid daily dose, the daily oral steroid dosage for the subject could be reverted to the preceeding daily dosage instructed by the investigator, but should not exceed Baseline dose.

